4.4.1.1.5 Number of Days of Occurrence

Number of days of occurrence over the period considered is derived from the daily intensities computed as described in [Section 4.4.1.1.1](#). It corresponds to the number of days with daily intensities of Grade 1, Grade 2, or Grade 3. Number of days of occurrence on the solicited period with a specified intensity may also be derived.

Number of days of occurrence during the solicited period will be displayed by category (range) as follows:

- Injection site reactions (D0-D7): 1-3 days, 4-7 days, 8 days
- Systemic reactions (D0-D14): 1-3 days, 4-7 days, 8-14 days, 15 days

4.4.1.1.6 Overall Number of Days of Occurrence

If a reaction is ongoing at the end of the solicited period, then the overall number of days of occurrence is derived from the daily intensities and the stop date of the reaction after the end of the solicited period. The overall number of days of occurrence is:

- $(\text{stop date} - \text{last vaccination date}) + (\text{number of days of occurrence within the solicited period}) - \text{length of the solicited period} + 1$

If the stop date is missing or incomplete (contains missing data [MD]), the overall number of days of occurrence will be considered as Missing.

Overall number of days of occurrence will be displayed by category (range) as follows:

- Injection site reactions (D0-D7): 2-3 days, 4-7 days, ≥ 8 days, missing
- Systemic reactions (D0-D14): 2-3 days, 4-7 days, 8-14 days, ≥ 15 days, missing

4.4.1.1.7 Ongoing

Ongoing is derived from the last daily intensity of the solicited period computed as described in [Section 4.4.1.1.1](#) and the maximum intensity on the ongoing period. The investigator's ongoing flag is not used because the measurement would determine the ongoing status of the reaction.

- Ongoing: if the last daily intensity of the solicited period is at least Grade 1 and the maximum intensity on the ongoing period is at least Grade 1
- Not ongoing: if the last daily intensity of the solicited period is None or the maximum intensity on the ongoing period is None.

- Missing: all other conditions (in this case, it is not included in the denominator of the ongoing analysis in the safety tables).

4.4.1.2 Unsolicited AEs

An observation will be considered as an event if it has at least a verbatim term and is not a Grade 0 intensity event. Grade 0 events should be included in the listing “Unsolicited adverse events not included in the safety analysis”.

4.4.1.2.1 Intensity

Intensity will be derived according to the following classification: None, Grade 1, Grade 2, Grade 3, or Missing.

If the unsolicited AE is measurable and its preferred term is part of the list of solicited reactions, then the measurement is derived based upon and following the same rule than the intensity scales defined in the protocol for that measurable injection site or systemic reaction.

Intensity for the other unsolicited AEs will correspond to the value reported in the CRF.

The maximum intensity corresponds to the highest intensity for a unique term.

4.4.1.2.2 Last Vaccination

Last vaccination before an unsolicited AE is derived from the start date of the unsolicited AE provided in the CRF and is calculated as follows:

- If an unsolicited AE has a complete start date and different to any the vaccination date, the start date is used to determine the last vaccination before the unsolicited AE
- If the start date is missing or partially missing, or equal to any vaccination date, then the visit number in the “appeared after visit” or similar field, is used to determine the last vaccination before the unsolicited AE

4.4.1.2.3 Time of Onset

Time of onset is derived from the start date of the unsolicited AE and the date of last vaccination:

- start date of the unsolicited AE - date of previous vaccination

The time of onset should be considered as missing only if one or both of the dates are missing or partially missing.

The unsolicited AEs will be analyzed “Within 28 days”, which corresponds to AEs with a time of onset between 0 and 28 days after vaccination or missing. An AE with missing time of onset will be considered to have occurred just after the vaccination indicated by the visit number, so will be included in these tables.

Note: Unsolicited AE that occurred before vaccination (negative time of onset) or with a time of onset higher than defined above will not be included in analysis, but will be listed separately.

Time of onset will be displayed by period as follows: D0-D3, D4-D7, D8-D14, \geq D15 and Missing.

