9.1.1.3 Safety Assessment Methods

At each vaccination Visit, the Investigator or a delegate will perform a clinical or medically-driven physical examination, and will ask the subject about any solicited reactions and unsolicited AEs recorded in the diary card, as well as about any other AEs that may have occurred since the previous Visit. All relevant data will be transcribed into the CRB according to the instructions provided by the Sponsor.

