5.3.1.5 Start Date and Stop Date

Missing or partially missing start dates for unsolicited AEs will remain missing and not be imputed. If the start is missing or partially missing, the time of onset will be considered to be missing. Nevertheless, unsolicited AEs with missing time of onset will be included in analyses according to the visit number collected in “Appeared after visit” or similar field. If either the start date or end date is missing or partially missing, the duration will be considered missing.

Missing or partially missing stop dates for AEs (solicited reactions and unsolicited AEs) will remain missing and not be imputed.

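### Unsolicited AEs with a partial start date are counted as within 28 days of the last injection even when the known month shows a later onset

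*SAP*

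**What the plan says.** Three sections of the SAP act together.

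- **4.4.1.2.2, Last Vaccination.** For an event whose start date is incomplete, or falls on an injection day, the number of the visit after which it appeared "is used to determine the last vaccination before the unsolicited AE". The visit number therefore selects an injection. It is given no other task here.
- **4.4.1.2.3, Time of Onset.** "The time of onset should be considered as missing only if one or both of the dates are missing or partially missing". The within-28-days tables then take in every event with a computed onset of day 0 to 28 and add every event whose onset could not be computed. The justification is a convention: "An AE with missing time of onset will be considered to have occurred just after the vaccination indicated by the visit number". A note then removes events whose onset is negative or beyond the window and sends them to a separate listing.
- **5.3.1.5, Start Date and Stop Date.** The missing-data section leaves incomplete dates as they stand, without imputation, and repeats the consequence: "If the start is missing or partially missing, the time of onset will be considered to be missing". Such events still enter the analyses, by visit number.

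The protocol's primary endpoint (9.1.1.2) limits unsolicited AEs to the first 28 days following each injection. SAP 4.4.1.3 and 4.4.1.4 split SAEs and AESIs into a 28-day period and later periods, but neither says where an event with missing onset belongs.

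**The concern.** A partial date is not the same as no date. When the month and year are known, they can prove that an event started outside the window, and the rule discards that proof. Two events with equally certain late onset are then handled in opposite ways: the fully dated one is excluded and listed, and the one lacking only its day is placed directly after the injection.

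The primary objective is to describe safety after each injection, so these dose-specific tables are the main output. A late event counted early inflates them. If the same onset rule were used for SAEs and AESIs, it would also take the event out of the later period where it belongs.

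Such records can arise. At vaccination visits the investigator asks about diary-card events "as well as about any other AEs that may have occurred since the previous Visit" (Protocol 9.1.1.3). Visits 5 and 7 come about five months after the preceding visit. Diary cards 2 and 4 cover those gaps, and the memory aid covers the final follow-up.

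**Working it through.** The rule has no figure of its own to reproduce. The only design figure, a 95% chance of seeing an event of 3% incidence among 100 vaccinees, does reproduce (1 − 0.97^100 = 0.952), but it does not bear on this point. The check is to apply the SAP's rules to example records.

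**Record A: month known, day missing.** Assume injection 1 on 10 January and a start date giving only May of the same year.

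1. Injection 2 is due at month 6 ± 20 days, so no earlier than about 20 June. All of May lies before it, and the last vaccination is injection 1.
2. Onset is Missing, because the start date is partial.
3. Missing is included in the window, so the event is tabulated within 28 days of injection 1.
4. The earliest possible onset is 1 May. From 10 January it is 22 days to 1 February, 22 + 28 = 50 to 1 March, 50 + 31 = 81 to 1 April and 81 + 30 = 111 to 1 May (112 in a leap year).
5. The exclusion note cannot act, since it needs a computed onset and there is none.

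**Record B: the same event dated 3 May.** Onset is 111 + 2 = 113 days. It exceeds 28, so the event is excluded and listed. Records A and B differ only in a missing day of the month.

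**Record C: partial date that does not settle the question.** With only February known, the earliest onset is day 22, inside the window. Counting it is a reasonable cautious default.

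**Record D: no date, appeared after Visit 4.** Visit 4 is planned for day 28 to 42. If it was held on day 31, onset was day 31 or later, yet the event is counted within 28 days. This case arises only if the CRF field can hold Visit 4, 6 or 8. The SAP does not show which visits it accepts.

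**Effect of one misplaced event.** Percentages count subjects, so an event changes a row only if that subject is not already in it. For an otherwise empty row (Clopper-Pearson 95% CI):

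| Group | Without the event | With the event |
|---|---|---|
| Vaccine, n = 100 | 0% (0 to 3.6%) | 1% (0.03 to 5.4%) |
| Placebo, n = 50 | 0% (0 to 7.1%) | 2% (0.05 to 10.6%) |

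**The case against.** The strongest defence is that this is a disclosed, cautious convention. It applies identically to both groups, tends to overcount early events, and no hypothesis is tested. The onset display has its own Missing row. All of that is true, and inclusion should stay the default when timing is truly unknown. It does not justify counting an event as early when the record shows that it was late. The Missing row gives the number of incomplete dates but does not separate unknown onset from known-late onset.

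A second defence is that few such records should exist, and this limits the size. Start dates must be recorded, SAEs are reported within 24 hours with supporting records and reconciled with the pharmacovigilance database, and queries are closed before lock.

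Three stronger readings are tempting, and the documents do not support them.

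- *Most late study time is exposed to the error.* Of about 548 days, 3 × 29 = 87 fall in a window and 461 (84%) do not. That is calendar time, not a misclassification share, because non-serious unsolicited AEs are planned for collection only on days 0 to 28.
- *The SAE and AESI tables are affected.* SAP 4.4.1 defines an SAE as a kind of unsolicited AE, so the onset rule may carry over. However, 4.4.1.3 and 4.4.1.4 do not invoke it, and placement by visit number in 5.3.1.5 could be read as allowing the later period. This is a gap, not a stated error.
- *Late events will be reported as related and early.* Setting missing causality to related (5.3.1.2) requires a second missing field in the same record.

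**Conclusion.** The point holds for partial dates whose known month and year exclude days 0 to 28. There the SAP states a rule that gives a wrong result and contradicts its own treatment of the same event when fully dated. It holds for appeared-after visits only if the CRF field can record a visit that was itself held after day 28. For SAEs and AESIs, the finding is that the placement of events with missing onset is unspecified, so two programmers could put the same event in different periods.

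The practical effect is probably small. It falls mainly on late-reported events and, if the rule is carried over, on SAEs and AESIs. The documents give no rate of partial dates, so no overall size can be stated, and at a rate of zero there is no effect. The per-event figures assume a row that would otherwise be empty.

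**What to change.** Amend SAP 4.4.1.2.3 to read: *An AE with missing time of onset is included in Within 28 days unless the known part of its start date, or the actual date of its appeared-after visit, shows that onset was more than 28 days after the last vaccination.* Using the actual visit date, not the nominal one, keeps an event that may have begun on day 28 after a visit held that day.

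Three consequential edits are needed:

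- Non-serious AEs excluded by this check go to the existing separate listing, since they have no later analysis period.
- SAEs and AESIs excluded by it go to the matching later period in 4.4.1.3 or 4.4.1.4, and both sections should say so.
- Section 5.3.1.5 should state that the known part of a partial date is used for this check only and that nothing is imputed.

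Record C stays in the window as now. The cost is short edits to four SAP sections, a little more programming on fields already collected, and a small departure from a standard sponsor convention, which should be recorded in SAP 5.7.

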4.4.1.2.4 Duration

Duration is derived from the start and stop dates of the unsolicited AE provided in the clinical database:

- stop date of unsolicited AE – start date of unsolicited AE + 1.

The duration should be considered as missing only if one or both of the start and stop dates of the unsolicited AE is missing or partially missing.

Duration will be displayed by period as follows: 1-3 days, 4-7 days, 8-14 days, 15 days or more, Missing.

4.4.1.3 SAEs

An event will be considered as a serious event if “Yes” is checked for “Serious” in the CRF.

SAEs will be analyzed throughout the study using the following periods:

- Within 28 days after each injection
- Between 28 days after last injection and next injection
- During the 6-month follow-up period (ie, from 28 days after last injection until the last subject contact)
- During the study (ie, all SAEs occurred during the study)

4.4.1.4 AESIs

An event will be considered as an AESI if “Yes” is checked for “Is the event an AESI?” in the CRF.

AESIs will be analyzed throughout the study using the following periods:

- Within 28 days after each injection
- Between 28 days after last injection and next injection
- During the 6-month follow-up period (ie, from 28 days after last injection until the last subject contact)
- During the study (ie, all AESIs occurred during the study)

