9.1.1.2 Safety Endpoints

The primary endpoints for the evaluation of safety are:

- Occurrence of any unsolicited systemic AE reported within 30 minutes after each injection
- Occurrence of solicited (ie, pre-listed in the subject's DC and in the CRB) injection site reactions (pain, erythema, and swelling) occurring up to 7 days after each injection
- Occurrence of solicited systemic reactions (fever, headache, malaise, myalgia, and asthenia) occurring up to 14 days after each injection
- Occurrence of unsolicited AEs occurring up to 28 days after each injection
- Occurrence of serious and non-serious AESIs in defined time windows according to the type of AESI
- Occurrence of SAEs throughout the trial (ie, from D0 through the end of the study)
- Occurrence of hospitalized VCD cases throughout the study (ie, from D0 through the end of the study)

Other endpoints will be recorded or derived as described in the Statistical Analysis Plan. Depending on the item, these could include: nature (Medical Dictionary for Regulatory Activities [MedDRA] preferred term), time of onset, duration, number of days of occurrence, Grade of severity, relationship to vaccine, action taken, whether the event/reaction led to early termination from the study, seriousness, or outcome.

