9.1.1.3.4 Adverse Events of Special Interest

Serious AESIs

The following serious AESIs will be considered:

- Serious hypersensitivity/allergic reactions occurring in all subjects within 7 days after vaccination
- Serious viscerotropic disease occurring in all subjects within 30 days after vaccination
- Serious neurotropic disease occurring in all subjects within 30 days after vaccination
- Serious dengue disease requiring hospitalization^a occurring in all subjects at any time during the study

Specific guidelines are provided to the Investigator to help in the assessment of AEs that may be indicative of viscerotropic or neurotropic disease (see Guidelines for Assessing Viscerotropic and Neurotropic AE).

^a A hospitalized subject is any subject admitted to hospital or any healthcare institution and providing in-patient care.

Non-Serious AESIs

The following non-serious AESIs will be considered:

- Hypersensitivity/allergic reactions occurring in all subjects within 7 days after vaccination.

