5.1.1.2 Statistical Methods

All analyses will be descriptive. Safety will be assessed after each and any dose of CYD Dengue vaccine.

For the main parameters, 95% CIs of point estimates will be calculated using the normal approximation for quantitative data and the exact binomial distribution (Clopper-Pearson method) for single proportions.

The analysis of safety will address the number and percentage of subjects with injection site or systemic AEs until 28 days following each injection (solicited systemic reactions from D0 to D14, solicited injection site reactions from D0 and D7 and unsolicited AEs until D28, including AESIs and immediate unsolicited AEs, ie, occurring within 30 minutes after each vaccination).

Solicited reactions will be described according to their intensity and according to time of onset, number of days of occurrence, action taken, and according to whether they lead to trial discontinuation.

Unsolicited AEs will be described by Medical Dictionary for Regulatory Activities (MedDRA) SOC and preferred term definition according to their relationship, severity, time to onset, leading to study discontinuation and duration.

Serious and non-serious AESIs (in defined time windows according to the type of AESI) and SAEs (throughout the trial; including the 6-month follow-up) will be described by MedDRA SOC and preferred term, outcome, seriousness and relationship to vaccination.

The number and percentage of subjects with a hospitalized suspected dengue cases virologically-confirmed at any time throughout the trial after the injection will be described.

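### None of the four AESI periods in SAP 4.4.1.4 is the 7-day or 30-day window of the primary AESI endpoint, so a viscerotropic or neurotropic event on day 29 or 30 is tabulated away from its injection

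*SAP*

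**What the plan says.** Protocol 9.1.1.2 lists among the primary safety endpoints "Occurrence of serious and non-serious AESIs in defined time windows according to the type of AESI". Protocol 9.1.1.3.4 supplies the windows for serious events. Allergic reactions have 7 days. For viscerotropic disease the text is "Serious viscerotropic disease occurring in all subjects within 30 days after vaccination", and neurotropic disease has the same 30 days. Hospitalized dengue counts when "occurring in all subjects at any time during the study". The only non-serious AESI type is again allergic, with the same 7 days. The notes to SAP Table 3.1 repeat these windows as the rule for what sites report.

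SAP 5.1.1.2 carries the windows into the analysis. Its AESI sentence begins "Serious and non-serious AESIs (in defined time windows according to the type of AESI" and goes on to description by system organ class, preferred term, outcome, seriousness and relationship.

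SAP 4.4.1.4 is the derivation section for AESIs. It identifies an AESI by the CRF tick-box alone and sets four analysis periods. The first is "Within 28 days after each injection". The other three are from 28 days after an injection to the next one, the 6-month follow-up (starting 28 days after the last injection), and the whole study. These are the same four periods that SAP 4.4.1.3 sets for SAEs. SAP 5.7, which records changes to the planned analyses, says nothing about AESI windows.

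**The concern.** The endpoint and the methods text are defined by type-specific windows, while the derivation rule uses periods that do not depend on type. A programmer who follows 4.4.1.4 will not produce what 5.1.1.2 promises, and nothing in the SAP says how the two relate.

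The mismatch matters most for viscerotropic and neurotropic disease. Protocol 1.3.2 singles these out as a risk to be considered because the vaccine has a yellow fever backbone, and the population here is HIV-positive. Few such events are expected, so the table position of a single event can decide whether a within-window count reads 0 or 1. The primary objective (Protocol 2.1, SAP 2.1) is to describe the safety of each injection, and the 28-day row is the only one in 4.4.1.4 defined as a fixed interval after each injection.

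**Working it through.** No design figure depends on this point. For completeness, the plan's one design figure does reproduce: with 100 vaccinees and a true incidence of 3%, P(at least one event) = 1 − 0.97^100 = 0.952, against the stated 95%. The check itself is a comparison of windows.

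**Step 1. Match each window to a listed period.**

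| AESI type | Window (Protocol 9.1.1.3.4) | Matching period in SAP 4.4.1.4 |
|---|---|---|
| Allergic, serious or non-serious | 7 days | none |
| Viscerotropic, serious | 30 days | none |
| Neurotropic, serious | 30 days | none |
| Hospitalized dengue | whole study | whole-study row |

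**Step 2. Classify by onset day.** SAP 4.4.1.2.3 takes onset as start date minus date of the previous vaccination and treats 0 to 28 as within 28 days. The same count is used here.

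| Onset day | In 7-day window | In 30-day window | Row by time in 4.4.1.4 | Whole-study row |
|---|---|---|---|---|
| 5 | yes | yes | within 28 days | yes |
| 8 | no | yes | within 28 days | yes |
| 28 | no | yes | within 28 days | yes |
| 29 | no | yes | between injections, or follow-up | yes |
| 30 | no | yes | between injections, or follow-up | yes |
| 31 | no | no | between injections, or follow-up | yes |

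**Step 3. Size of the split.** D0-D30 contains 31 days. Days 29 and 30 fall outside the 28-day row: 2/31 = 6.5% of the window. This is a share of days. Reading it as a share of events would require uniform onset over the window, which the documents do not give.

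**Step 4. The allergic window.** Days 8-28 are 21 of the 29 days D0-D28 (21/29 = 72.4%). An allergic event in that span enters the 28-day row only if it carries an AESI flag, which the 7-day reporting rule does not allow. The documents describe no check of the flag against onset day or type. By contrast, for unsolicited AEs SAP 4.4.1.2.3 works from dates and lists out-of-window events separately.

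**The case against.** The case for leaving the SAP alone has four parts.

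First, a reader who saw only the first bullet might infer that AESIs are counted in a single 28-day period. The section does not say that. It lists four periods, and the last takes in every flagged AESI. This stands.

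Second, a reader might infer that the tabulated endpoint is no longer the one the protocol defines. The windows are part of the reporting rule in the notes to Table 3.1. If sites follow it when ticking the flag, the whole-study row contains exactly the window-defined AESIs, and for hospitalized dengue it matches the window outright. This stands for the whole-study count. It does not answer the per-injection question, because that row does not attribute events to an injection, and the row that does cuts the 30-day window at day 28.

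Third, the 28-day row has a basis in the plan. Protocol 12.1.1.2 and SAP 5.1.1.2 both include AESIs in the safety summary up to D28. This also stands, and it is why that row should not be replaced.

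Fourth, the allergic day 8-28 case requires a flag ticked against the protocol, which the blind data review before database lock might catch. That is fair: it is a secondary weakness of relying on the flag alone, not an error the rule produces by itself.

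What the objection does not remove is the day 29-30 case. There the flag is correct, the reporting rule has been followed, and the stated derivation still puts the event in a row that does not show it as falling within its post-injection window.

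**Conclusion.** The inconsistency between SAP 4.4.1.4 and the primary endpoint, and between 4.4.1.4 and SAP 5.1.1.2, is real, undeclared in 5.7, and small in effect. Three of the four serious AESI types, and the non-serious allergic type, have no row matching their window. The only misplacement that follows from the rule as written is a viscerotropic or neurotropic event with onset on day 29 or 30. Such an event moves between rows and remains in the whole-study total. A change from 0 to 1, or the reverse, can therefore occur in a per-injection count but not in the study total.

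The documents do not support the stronger claim that AESIs are lost, or that the primary endpoint has been replaced. No hypothesis is tested, so no inference, power or sample size changes. The study-hold rule in Protocol 5.5 counts related SAEs, including serious AESIs, without reference to these rows.

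The conclusion assumes that onset day is counted as in SAP 4.4.1.2.3 and that tables are programmed from 4.4.1.4 as written.

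**What to change.** In SAP 4.4.1.4:

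- Keep all four existing rows, including the 28-day row and the whole-study row.
- Add per-injection rows by AESI type using the protocol's own windows: allergic D0-D7, and viscerotropic and neurotropic D0-D30. Add a hospitalized dengue row covering the whole study.
- Derive the new rows from onset date and AESI type as well as the CRF flag, and state how a missing onset date is handled (the convention in 4.4.1.2.3 could be reused).
- List flagged events that fall outside their window separately.
- Add a cross-reference between 4.4.1.4 and 5.1.1.2 so that the two sections describe the same tables.

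The cost is SAP wording and table shells. The change needs only onset date, AESI type and the existing flag. It adds no new window and alters nothing at the sites.
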